
interactive, including games and recorded vignettes, as well as questions to gage children's comprehension of the concepts being presented. To collect pilot data, we created a very preliminary version of this computerized intervention to collect pilot data in young children. This preliminary intervention can be viewed at: https://www.youtube.com/watch?v=1wUNqdQ91Io&t=10s.

The parent version of the intervention will include these same basic concepts, but will also target parenting style and provide psychoeducation on the negative impact of over-reacting to children's mistakes. The parent version will also include examples of how to model appropriate reactivity to mistakes, and provide video vignettes and examples of both critical and adaptive parenting reactions to mistakes. The parent intervention will also provide feedback to the parent on how reactive they tend to be to their children's errors and provide a structured way for parents to plan to reduce their reactivity to their children's mistakes. For example, planning positive reinforcement strategies and how to avoid criticality in specific situations. We will also explore various motivations that parents may have for hyper-reactivity to children's errors (for example, the motivation to punish errors vs. preventing the child from failing and experiencing negative emotions) and discuss ways to increase awareness of these motivations, as well as the negative consequences of this behavior on children. Additionally, we will offer replacement behaviors, as well as examples of how to integrate these new behaviors into daily activities. Both interventions will be designed to last approximately 45 minutes. The format of the interventions will be based on [name] previous work using brief-computerized interventions. We will also consult with Drs. [name], [name], and [name], who all have expertise in the design of parenting interventions. Additionally, as stated above, we will provide parents in the active condition with weekly reminders and additional online materials. We have created a preliminary version of this computerized intervention for our pilot sample. This preliminary intervention can be viewed at:

```
https://www.youtube.com/watch?v=3qN0Hco17VI.
```

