Once an individual has been assessed for suicide risk, we will take the following actions, as suggested by Joiner et al. (1999) and Chu et al. (2015):

In addition, if children and/or their parents endorse experiencing significant psychological distress (e.g., significant anxiety or depression) during any portion of the study, the participants will be offered referral information for psychotherapy and/or pharmacologic treatment at Florida State University and the surrounding community. Participants who are initially enrolled in the study

will not be excluded from completing study procedures if they begin receiving treatment during the study. Because information relating to child abuse may be assessed, the staff will follow federal and state child abuse reporting requirements. Participants will be informed of the need to report child abuse prior to eliciting this information. In case of any reported abuse by the child or parent, the parents will be informed about the federal mandated reporting laws, verbally and in writing. In cases where it is necessary to make a child abuse report, the family will always be informed prior to contacting any state agency, and given the option of making a self-referral to protective services.

6.3 EEG, self-report, observational video data, and clinical interviews will be collected.

Self-report. The current proposal will utilize dimensional measures of anxiety symptoms measured by the Screen for Child Anxiety Related Emotional Disorders (SCARED) questionnaire. Both the parent and child will complete the SCARED regarding anxiety symptoms experienced by the child before and after the treatment at the baseline assessment, and at the follow-up assessment.

To capture a broad spectrum of symptoms, we will also administers the Child Behavior Checklist (CBCL) at the baseline and follow-up assessment. The CBCL is a 113-tiem parent-report checklist that assesses emotional and behavioral problems (internalizing and externalizing) over the past 6 months. We will utilize the depression scale from this measure, as well as the obsessive compulsive scale.

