Give child the Picasso Tiles and give the parent the images. Tell the participants they can start and set the 3 minute timer and record the episode .

When timer goes off, enter the room and tell the family that they did a great job and that now it is time to start a new activity.

Episode 4: Negative Discussion.

"For this activity, we want you to talk together about a time this week when _____

(child's name) did something wrong. If you can't think of something from this week, you can talk about the most recent situation that you can remember. You will have 3 minutes to have this discussion. Do you have any questions?"

Tell the participants that they can start and set the 3 minute timer and record the episode . When timer goes off, enter the room and tell the family that they did a great job and that now it is time to start a new activity.

Episode 5: Positive Discussion.

"For this activity, we want you to talk together about a time this week when

(child's name) did something right. If you can't think of something from this week, you can talk about the most recent situation that you can remember. You will have 3 minutes to have this discussion. Do you have any questions?"

Tell the participants that they can start and set the 3 minute timer and record the episode . When timer goes off, enter the room and tell the family that they did a great job and that now it is time to start a new activity.

The parent and child will be given directions for each task (which will last approximately 2 - 3 minutes) while being video-taped. The videos will be coded for sensitivity to mistakes (modified from [name] coding schemes). For example, negative or positive statements regarding errors or imperfections will be coded (e.g., I hate making mistakes, I'm bad, I'll never do this right, etc.). After meeting with [name] at her lab for training on this approach, I will train a team of coders (undergraduate assistants) to code these observations reliably and use Mangold coding software to track codes second by second and to do reliability analyses.

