EEG data processing and analyses. While participants complete the Go/No-Go task, EEG will be recorded from 32 scalp locations. The response-locked ERPs will be averaged separately for each trial type (e.g., correct and incorrect responses), and baseline correction will be performed using the interval from -500 to -300 ms before response commission. Average activity at three electrode sites (FCz, Cz, and Fz) between 0 and 100 ms after the response will be exported for each subject – we have previously shown that this is where the ERN is maximal and most reliable in children 82. In order to obtain a measure of differentiation between errors and correct responses, the average activity on correct trials will be subtracted from the average activity on error trials (i.e., the ERN). Procedure. Research assistants will explain the study to parents and children and obtain consent for participation. Families will be randomized to a group (parent only, child only, parent/child, or control). Parents and children will participate in a brief observational task and complete questionnaires. Children will then complete the go-no/go task. After this, a trained research assistant will guide the child through the computer intervention or control. After the intervention, children will complete the go-no/go task again, and complete the observational task and questions. Simultaneously, parents will be completing questionnaires and will be administered the intervention or control. The first lab assessment will take approximately 2 - 3 hours.

The second lab assessment will take place approximately 6 months later. At this lab visit, both parents and children will complete follow-up questionnaires and behavioral observation. Additionally, children will complete the go-no/go task.

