Clinical Interviews. We plan to conduct two clinical interviews with the parent, at each lab visit. Both interviews are assessments we routinely utilize in our research studies at FSU and will be conducted by a research assistant or graduate student who is trained in the administration of these interviews and has demonstrated reliability. We plan to complete the Schedule for Affective Disorders and Schizophrenia for School-Age Children: Present and Lifetime Version (K-SADS-PL: Kaufman, Birmaher et al., 1997) with the parent regarding the child's symptoms. Additionally, we plan to complete the Mini-International Neuropsychiatric Interview (MINI SCID) with the parent regarding the anticipate that these interviews (together) will take approximately 30 - 40 minutes to complete. As in previous studies, the interviews will be audio recorded for the purposes of coding reliability. Participants will be asked if it is ok to record the interview before each interview begins.

6.4 There is no plan for follow-up after the second lab assessment.

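### As written, families are randomised after consent but before the baseline measures, and nothing keeps the arm concealed until baseline is complete

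*Combined protocol and SAP*

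**What the plan says.** The Procedure paragraph in section 6.3 is the only step-by-step account of the first visit. After consent it reads: "Families will be randomized to a group (parent only, child only, parent/child, or control). Parents and children will participate in a brief observational task". It continues, after the baseline questionnaires: "Children will then complete the go-no/go task. After this, a trained research assistant will guide the child through the computer intervention or control". On the parent's side it says: "Simultaneously, parents will be completing questionnaires and will be administered the intervention or control".

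Section 22.1 confirms that consent is taken at the start of the visit. Sections 3.3 and 6.1 mention randomisation without timing it. No section says how the assignment is generated, who holds it, when it is opened, or whether families, research assistants, video coders or interviewers are unaware of it. The nearest text is in section 5.0: the control is a computerised presentation in the same format as the active module, given to parents and children.

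The measures taken before the module include the child and parent error-sensitivity scales, the videotaped parent-child tasks and the SCARED: "Both the parent and child will complete the SCARED regarding anxiety symptoms experienced by the child before and after the treatment".

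Sections 10.2 and 13.3 make a raised score on the child or the parent error-sensitivity index a recruitment criterion. That screen appears to come before randomisation.

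**The concern.** Baseline is a clean reference only if nobody's answers or behaviour can depend on the arm. A parent who knows that the assigned module deals with reactions to a child's mistakes may complete the error-sensitivity scale differently, or behave differently on camera. Staff who know the arm may prompt differently. A difference created at baseline in this way, and gone by the later assessment, is counted as treatment change. Its direction is unknown, so it could imitate a benefit or hide one.

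The outcomes exposed are the self-report, parent-report and observed measures in Aims 1a, 2c and 3. The ERN, averaged over fixed electrode sites and a fixed 0-100 ms window, is much less open to this.

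The second consequence needs no assumption about who knows the arm. Under the written order, a dyad that stops during the observation, the questionnaires or the 200-trial EEG task has already been randomised. It becomes a post-randomisation loss without having received anything.

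**Working it through.** **Order of events.** Reading the Procedure paragraph sentence by sentence gives: consent; randomisation; observational task and questionnaires; first go/no-go task; module; repeat measures. Explicit time words begin only at the go/no-go task, so the place of randomisation rests on sentence position. No other section gives a different place.

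**Losses.** Section 6.1 allocates 50, 50, 50 and 25. One dyad lost between randomisation and baseline is 1/25 = 4% of the control arm and 1/50 = 2% of an active arm.

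**Illustrative size.** The documents give no shift, no pre-post correlation and no analysis model (section 17.1 restates the aims), so there is no figure of the plan's own to reproduce. Assumptions: no true effect; equal SDs at both times; a baseline shift d of 0.1 or 0.2 SD in the active dyads relative to control; correlation r from 0.4 to 0.8; a share p of the shift persisting at the later assessment because the arm is known then; 150 v 25 dyads; two-sided nominal 5% test.

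- SE = sqrt(1/150 + 1/25) = 0.2160
- Rejection rate = Φ(b − 1.96) + Φ(−b − 1.96)
- Written order, change score: b = (1 − p)d / (SE × sqrt(2(1 − r)))
- Written order, baseline-adjusted: b = |p − r|d / (SE × sqrt(1 − r²))
- After the fix the baseline shift is zero and the later shift is pd. Change score: b = pd / (SE × sqrt(2(1 − r))). Adjusted: b = pd / (SE × sqrt(1 − r²))

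Worked ends of the range for a wholly transient shift (p = 0):

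- d = 0.1, r = 0.4: change b = 0.1/(0.2160 × 1.0954) = 0.423, rate 7.1%; adjusted b = 0.04/(0.2160 × 0.9165) = 0.202, rate 5.5%
- d = 0.2, r = 0.8: change b = 0.2/(0.2160 × 0.6325) = 1.464, rate 31.0%; adjusted b = 0.16/(0.2160 × 0.6) = 1.234, rate 23.5%

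Rejection rates over r = 0.4 to 0.8:

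| Shift; share persisting | Change, as written | Change, after fix | Adjusted, as written | Adjusted, after fix |
|---|---|---|---|---|
| 0.1 SD; none | 7.1-11.3% | 5% | 5.5-9.5% | 5% |
| 0.2 SD; none | 13.5-31.0% | 5% | 6.9-23.5% | 5% |
| 0.2 SD; half | 7.1-11.3% | 7.1-11.3% | 5.0-7.5% | 8-12% |
| 0.2 SD; all | 5% | 13.5-31.0% | 6-9% | 17-34% |

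In the half-persisting row the change-score bias keeps its size and reverses its sign. With the 155 dyads expected at six months (section 25.1) in the same ratio, SE = 0.2295, and the wholly transient ranges become about 7-28% (change) and 5-21% (adjusted).

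**Visit time for the parent.** The inputs are two observation blocks of five episodes at up to 3 minutes (2 × 15 = 30 minutes; "The parent and child will be given directions for each task (which will last approximately 2 - 3 minutes) while being video-taped"), the interviews ("We plan to conduct two clinical interviews with the parent, at each lab visit"; "these interviews (together) will take approximately 30 - 40 minutes to complete") and the module ("Both interventions will be designed to last approximately 45 minutes"). The total is 30 + (30 to 40) + 45 = 105 to 115 minutes in any order. That leaves 65-75 minutes of a 3-hour visit, or 5-15 minutes of a 2-hour visit, for consent, questionnaires and other untimed steps.

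**The case against.** The strongest reply is that the point rests on silence and sentence order. The randomisation sentence has no time marker, and nothing says that the assignment is disclosed when it is made. This stands. A reader might infer that families and staff know the arm during baseline, or that the baseline scores are biased. The documents support neither; they leave the matter open.

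A reader might also infer that the main result is at risk. Section 5.0 names development of the intervention and testing its effect on the ERN as the primary goal, and the ERN tests in Aims 1 and 2 are largely spared. The same-format control also limits what families could deduce from the module itself, although it does not govern what is known before the module starts.

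The upper figure of 31% should not be read as the trial's false-positive rate, or as what reordering would save. It needs a 0.2 SD shift, a correlation of 0.8, change scores and a shift that vanishes by the later assessment. For Aim 1a the two assessments fall within one visit, so some persistence is plausible. Where the shift persists, reordering does not lower the rejection rate and can raise it, as the table shows. No section supports one pattern over the other.

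Finally, the eligibility screen may supply a pre-allocation score for the self-report error-sensitivity measures. That is a real mitigation for part of Aims 1a and 2c. It does not cover the SCARED or the observed measures.

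**Conclusion.** The point holds as a gap in a stated order, not as a demonstrated bias. Two benefits of changing the order do not depend on the illustration: the baseline cannot be influenced by the arm, and dyads that stop during baseline are not counted as losses from an arm in which one dyad is 4%. The effect on error rates is conditional on the assumed shift, correlation and persistence. Reordering restores 5% only if the shift is wholly transient. It protects the baseline and the accounting of losses, not later reports made once the arm is known. The sponsor should make the change because it is cheap. Confidence is medium, because the order is inferred from sentence position and the laboratory may already conceal the assignment in practice.

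**What to change.** In the Procedure paragraph of section 6.3, move the randomisation sentence to after the pre-intervention go/no-go task and the parent's baseline questionnaires, just before either module starts, and state which parent questionnaires count as baseline. If the assignment must be generated at consent, state that it stays concealed (sealed or electronic) from families and from staff collecting baseline until that point, and report dyads lost before the module by arm.

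The child's module already follows the first go/no-go task, so the child's sequence need not change. The cost falls on the parallel parent session: the parent module may start later, and the child may have to wait for the parent's baseline to finish. The fit to a visit of 2 to 3 hours must therefore be checked for parent and child, the more so because section 15.1 commits to keeping visits as short as the protocol allows. Interviews that are not counted as baseline can follow the module. Slightly fewer than 175 dyads may be randomised if some stop during baseline, but the number with a usable baseline is the same as under the present order.

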7.0 Data and Specimen Banking*

7.1 All information with identifying information collected during the project will be kept in a locked storage cabinet to which only [name] and the study coordinator will have access. All data will be stored separately from identifying information and will be password protected. No names will be maintained in data records; rather, information will be coded by ID numbers only. Each individual will receive a unique I.D. number thereby allowing handling of data on all subjects without using individual names. PI [name] will be responsible for monitoring the maintenance of confidentiality. In the event of a breach of confidentiality, he will inform the subject and his/her parents that the breach occurred; any breaches of confidentiality will be reported to the Institutional Review Board. Codifying participants by unique identifiers is an extensive practice that is highly efficient at protecting anonymous participation. No individual child or family will be identified in any publications or presentations of the research findings.

7.2 EEG data, self-report data, observation video data will be stored for each participant.

7.3 If a participant requests their data (EEG, self-report, or observational video data), we will provide a summary of relevant data, along with a brief description of the measure. Data will not be released to anyone other than a participant.

8.0 Sharing of Results with Subjects*

8.1 We do not plan to share results with participants (unless they request us to do so).

9.0 Study Timelines*

- 9.1 Describe:
 - Each subject will participate in the study for 6 months.
 - Year 1: intervention development, collect pilot data from 10 parent/child dyads.
 - Year 2 4: recruit and collect data from 6 parent/child dyads per month, total N = 175 parent/child dyads. We will also collect 6-month follow-up data in the lab for each parent/child dyad.
 - Year 5: complete all follow-ups. Data processing, analysis, statistical procedures and manuscript preparation.

10.0 Subject Population*

10.1 Participants in the study will be 175 parent and child dyads recruited using the Family Registry at Florida State University (FSU). I plan to recruit families with children between the ages of 5 and 7 years of age.

- 10.2 We plan to recruit parent/child dyads who are high in error sensitivity (as measured by the Child Error Sensitivity Index, selfreport). Because our intervention will be designed to target error sensitivity, we will recruit families who score at least .5 standard deviations above the mean on the Child Error Sensitivity Index or the Parent Sensitivity to Children's Errors Index. We will derive means and standard deviations from our previous study, which was conducted in this same age-range and community. Additionally, we will request that the primary caregiver accompany the child to the lab visit (i.e., spends at least 50% or more of total parenting time with the child). Prior to the in-lab visit, participants will complete an additional phone screen to determine whether they meet any Coronavirus-specific exclusion criteria. This phone screen will assess whether participants may have contacted Coronavirus and whether they are at higher risk for severe illness. Any participants who do not pass this screening will not be permitted to take part in the study.
- 10.3 This study will not include: adults unable to consent, pregnant women, prisoners. The study will include: children.

11.0 Vulnerable Populations*

11.1 This research study involves children between the ages of 5 – 7 years old. We will collect parental consent for all study procedures, as well as child assent. Additionally, children will be reminded throughout the lab visit that they can take a break or stop the study at any time.

12.0 Local Number of Subjects

12.1 175 parent/child dyads.

13.0 Recruitment Methods

13.1 Participants in the study will be 175 parent and child dyads recruited using the Family Registry at Florida State University (FSU) or a targeted mailing list. The FSU Center for Developmental Science implements on-going recruitment throughout the Tallahassee community, focusing on children and families. They maintain a database, which includes the names, ages, and contact information of children and families interested in participating in research studies. The Family Registry is comprised of over 1,500 families to date, and continues to grow each week due to regular recruitment events in the community. I plan to recruit families with children between the ages of 5 and 7 years of age. In addition to utilizing the Registry at FSU, I plan to post fliers in the community and recruit families at additional community events.

13.2 Source of recruitment: FSU Center for Developmental Science Family Registry and fliers that will be posted through-out the community. We also plan to utilize a targeted mailing list for children and families in the Tallahassee community.

We plan to recruit parent/child dyads who are high in error 13.3 sensitivity (as measured by the Child Error Sensitivity Index, self-report). Because our intervention will be designed to target error sensitivity, we will recruit families who score at least .5 standard deviations above the mean on the Child Error Sensitivity Index or the Parent Sensitivity to Children's Errors Index. We will derive means and standard deviations from our previous study, which was conducted in this same age-range and community. Additionally, we will request that the primary caregiver accompany the child to the lab visit (i.e, spends at least 50% or more of total parenting time with the child). If interested in participating, caregivers will complete an additional phone screen to determine whether they meet any Coronavirus-specific exclusion criteria. This phone screen will assess whether participants may have contacted Coronavirus and whether they are at higher risk for severe illness. Any participants who do not pass this screening will not be permitted to take part in the study.

13.4 The flier that we plan to use for recruitment will be attached to this submission. It includes a picture of a minions stuffed animal with an EEG

cap on. We state that families with children between the ages of 5 and 7 are eligible to participate in our study and provide our lab contact information. Additionally, we plan to send letters to families in the Tallahassee area who have children between the ages of 5 - 7 years old. This mailing list will be purchased from Direct Mail. The letter that we plan to send to potential participants will be attached to this submission.

13.5 The families will also receive a significant honorarium, \$60.00 for the baseline visit and \$60.00 for the follow-up assessment, and each visit should last no more than 3 hours. Providing the honorarium to the family, rather than the child, reduces the possibility that payment could be coercive—we leave it up to the parent to decide how to allocate the honorarium. If participants live more than 30 miles away, we will offer travel reimbursement of up to \$40. Additionally, families will be offered a t-shirt for parents and children for completion of the between assessment online modules.

